### 7.4 Final Study Visit

The approximate final study visit will occur at Week 4 for those subjects that enroll into the Open Label Extension study (ARQ-151-306), or Week 5 (Day 35 – Telephone Follow-up) for those subjects that do not enroll in ARQ-151-306. See Schedule of Visits and Assessments ([Section 2](#)).

## **7.5 Early Termination Visit**

If a subject is withdrawn or wishes to exit the study, a termination visit will be scheduled. This visit should include the procedures and assessments that would be performed at the Week 4 visit (Day 28).

## **7.6 Unscheduled Visit**

Unscheduled visits may be necessary to repeat testing following abnormal laboratory results, for follow-up of AEs, or for any other reason, as warranted in the judgement of the Investigator.

The following information will be collected for all subjects:

- Concomitant medications/procedures
- AEs

The following information also will be collected:

- IGA/I-IGA and PASI
- BSA affected with plaque psoriasis
- Local tolerability assessment (by Investigator)

The rules for how to tally IGA/I-IGA, BSA or other proportions of categorical responses will be described in the Statistical Analysis Plan.

## **7.7 Adverse Events**

### **7.7.1 Adverse Event Definition**

An AE means any untoward medical occurrence associated with the use of a drug in humans, whether or not considered drug related. An AE can therefore be any unfavorable and unintended sign (including an abnormal laboratory finding), symptom, or disease temporally associated with the use of a medicinal (investigational) product, whether or not related to the medicinal (investigational) product.

AEs will be collected following informed consent of the subject until one month after treatment.

A treatment emergent adverse event (TEAE) is defined as an AE that started post application of investigational product at the Baseline visit or was present at treatment initiation but worsened during treatment, through study completion.

Application site reactions will be considered adverse events if they require intervention, suspension or discontinuation of study drug.

### 7.7.2 Serious Adverse Event

The definitions and reporting requirements of the Food and Drug Administration (FDA)/ICH Guidelines for Clinical Safety Data Management, Definitions and Standards for Expedited Reporting, Topic E2A will be adhered to. If any AEs are serious, as defined by ICH Guidelines for Clinical Safety, required procedures will be followed. All SAEs will be reported to the Sponsor via fax or e-mail within 24 hours of becoming aware of the event, whether or not the serious events are deemed drug-related. All serious event reporting will adhere to ICH E6: Guideline for Good Clinical Practice and ICH E2A: Clinical Safety Data Management: Definitions and Standards for Expedited Reporting. The IRB will be notified of the Alert Reports as per FDA, ICH and the IRB's policies and procedures.

An SAE is any AE that in the view of either the PI or Sponsor, results in any of the following outcomes: Death, a life-threatening AE, inpatient hospitalization or prolongation of existing hospitalization, a persistent or significant incapacity or substantial disruption of the ability to conduct normal life functions, or a congenital anomaly/birth defect. Important medical events that may not result in death, be life-threatening, or require hospitalization may be considered serious when, based upon appropriate medical judgment, they may jeopardize the subject and may require medical or surgical intervention to prevent one of the outcomes listed in the above definition. Examples of such medical events include allergic bronchospasm requiring intensive treatment in an emergency room or at home, blood dyscrasias or convulsions that do not result in inpatient hospitalization, or the development of drug dependency or drug abuse.

Life-threatening is defined as an AE that in the view of the PI or Sponsor, places the subject at immediate risk of death. It does not include an AE that, had it occurred in a more severe form, might have caused death.

Hospitalization does not include the following:

- Rehabilitation facilities, hospice facilities or respite care (e.g. caregiver relief)
- Nursing homes or skilled nursing facilities
- Emergency room visits
- Same day surgeries (as outpatient/same day/ambulatory procedures)
- <24 hour admissions for observation or evaluation

Hospitalization or prolongation of hospitalization in the absence of a precipitating, clinical AE is not in itself an SAE. Examples include:

- Admission for treatment of a preexisting condition that did not worsen
- Hospitalizations for cosmetic elective surgery, social, and/or convenience admissions
- Pre-planned treatments or surgical procedures should be noted in the baseline documentation for the individual subject.

- Diagnostic and therapeutic procedures, such as surgery, should not be reported as AEs; however, the medical condition for which the procedure was performed should be reported if it occurs during the reporting period and meets the definition of an AE. For example, an acute appendicitis that begins during the AE reporting period should be reported as an AE, and the resulting appendectomy should be recorded as treatment of the AE.

Unexpected is defined as an AE that is not listed in the IB or is not listed at the specificity or severity that has been observed; or is not consistent with the risk information described in the general investigational plan or elsewhere in the IND.

If a SAE occurs to a subject on this study, contact the Sponsor personnel listed in Key Contacts List (provided separately) within one business day of knowledge of event.

### **7.7.3 Suspected Unexpected Serious Adverse Reaction (SUSAR)**

This is defined as a serious adverse reaction, the nature or severity of which is not consistent with the known study treatment information. A serious event or reaction is not defined as a SUSAR when: 'it is serious but expected' or it does not fit the definition of an SAE, whether expected or not.

### **7.7.4 Safety Review with Subject**

At each follow-up visit, subjects and/or caregivers will be queried with an open-ended question such as: 'How have you been feeling since your last visit?' Additionally, the study staff will review subject diaries and, if it appears that a potential AE was recorded, study staff will query the subject and determine if an AE occurred.

AEs (whether serious or non-serious) and clinically significant abnormal laboratory test value(s) will be evaluated by the PI and treated and/or followed up for up to one month after end of treatment until the symptoms or value(s) return to normal, or acceptable levels, as judged by the PI.

Where appropriate, medical test(s) and/or examination(s) will be performed to document resolution of event(s). Outcome may be classified as resolved, improved, unchanged, worse, fatal or unknown (lost to follow-up).

### **7.7.5 Adverse Event Reporting**

The PI will review each event and assess its relationship to drug treatment (unrelated, unlikely, possibly, probably, likely). Each sign or symptom reported will be graded on the NIH NCI CTCAE toxicity grading scale 5-point severity scale (Grade 1, 2, 3, 4 and 5). The date and time of onset, time relationship to drug dosing, duration, and outcome (resolved, improved, unchanged, worse, fatal, or unknown/lost to follow-up) of each event will be noted.

- The relationship of each AE to the study drug will be assessed using the following definitions:

Unrelated	
 
The AE must clearly be caused by the subject's clinical state, or the study procedure/conditions.
 
Definitely not related to drug.
 
Temporal sequence of an AE onset relative to administration of drug not reasonable.
 
Another obvious cause of an AE.
 

Unlikely	
 
Time sequence is unreasonable.
 
There is another more likely cause for an AE.
 

Possibly	
 
Corresponds to what is known about the drug.
 
Time sequence is reasonable.
 
Could have been due to another equally, likely cause.
 

Probably	
 
Is a known effect of the drug.
 
Time sequence from taking drug is reasonable.
 
Ceases on stopping the drug.
 
Cannot be reasonably explained by the known characteristics of the subject's clinical state.
 

Likely	
 
Is a known effect of the drug (e.g., listed in Physicians' Desk Reference, Compendium of Pharmaceuticals and Specialties, IB).
 
Time sequence from taking drug is reasonable.
 
Event stops upon stopping drug, event returns upon restarting drug.
 

- The following CTCAE toxicity grading scale 5-point severity scale definitions for rating maximum severity will be used:

Grade 1	Mild; asymptomatic or mild symptoms; clinical or diagnostic observations only; intervention not indicated.
Grade 2	Moderate; minimal, local or noninvasive intervention indicated; limiting age-appropriate instrumental activities of daily living.*
Grade 3	Severe or medically significant but not immediately life-threatening; Hospitalization or prolongation of hospitalization indicated; disabling; limiting self-care activities of daily living.**  Note: An experience may be severe but may not be serious, e.g., severe headache).
Grade 4	Life-threatening consequences; urgent intervention indicated.
Grade 5	Death related to AE.

Note: A semi-colon indicates 'or' within the description of the grade.

\* Instrumental activities of daily living refer to preparing meals, shopping for groceries or clothes, using the telephone, managing money, etc.

\*\* Self-care activities of daily living refer to bathing, dressing and undressing, feeding self, using the toilet, taking medications, and not bedridden.

AEs will be coded using the most current MedDRA® version available at the start of the study.

## 7.8 Reporting Pregnancy

During the study, all subjects should be instructed to contact the investigator immediately if they suspect they might be pregnant (e.g., missed or late menstrual period). If pregnancy is confirmed, the subject will be withdrawn from the study and followed until the pregnancy comes to term.

The investigator is responsible for reporting all available pregnancy information on the pregnancy report within 24 hours of becoming aware of the event, although pregnancy itself is not considered an AE. Study treatment must be discontinued immediately in the event of a pregnancy. The subject should be referred to an obstetrician/gynecologist experienced in reproductive toxicity for further evaluation and counseling. Monitoring of the subject should continue until the conclusion of the pregnancy. Follow-up information detailing the outcome of the pregnancy and the health of the newborn should be reported as it becomes available.

Should the pregnancy result in a congenital abnormality or birth defect, a SAE report must be submitted. Furthermore, all neonatal deaths that occur within 30 days of the birth should be reported as SAEs, without regard to causality. In addition, any infant death that occurs after the 30-day reporting period that the investigator suspects are related to the in-utero exposure to the study treatment should also be reported.

## 7.9 Treatment Stopping Rules

If a subject has non-cutaneous adverse events of concern, clinically significant laboratory values or any condition that the investigator determines could possibly be related to the study drug, the Investigator should immediately contact the Medical Monitor to discuss if the subject should be discontinued from the study.

Treatment for any individual subject will be discontinued if the subject:

- Experiences a serious adverse event (SAE) or a clinically significant non-serious AE which in the opinion of the Principal Investigator or Medical Monitor warrants discontinuation from the study for that subject's well-being.
- A severe (Grade 3) laboratory abnormality (confirmed by repeat sample and considered related to study drug; see [Appendix 5](#)).

Dosing of study drug for an individual subject may be suspended for safety concerns other than those described above, at the discretion of the investigator if he/she feels the subject's safety may be threatened.

CDI-2 raw total score of 34 should be referred promptly to a mental health care professional and consideration be given to discontinuation from study drug.

A subject that is experiencing suicidal ideation and behavior should be referred immediately to a qualified mental health care provider and consideration given to discontinuation from study drug.

As noted above, study treatment must be discontinued immediately in the event of a female subject's pregnancy.

Treatment should be interrupted:

- If a subject develops an application site reaction with the clinical appearance of an 'irritation reaction', and with a severity of a Dermal Response Score of 5 (erythema, edema and papules) or greater on the scale of Berger and Bowman, treatment should be interrupted for up to one week and may then be resumed if the reaction has, in the opinion of the Investigator, adequately resolved.

Treatment should be discontinued:

- If the reaction reoccurs, treatment should be discontinued permanently, and the subject followed until the reaction resolves.

For cases of suspected allergic contact dermatitis, the medical monitor and sponsor should be notified and there should be discussion about performing patch testing to further evaluate. Patch testing is encouraged in such cases.

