## **6.6 Removal of Subjects from the Study**

Subject participation in this trial may be discontinued for any of the following reasons:

1. Occurrence of any medical condition or circumstance that, in the opinion of the Investigator, exposes the subject to substantial risk and/or does not allow the subject to adhere to the requirements of the Protocol.
2. Occurrence of a treatment-emergent adverse event (TEAE) or considerable worsening of an AE that, in the opinion of the investigator in consultation with the Medical Monitor and Sponsor, represents an unacceptable risk to the subject if he/she continues in the study. The investigator must follow the subject until the AE resolves or satisfactorily stabilizes.
3. Pregnancy
4. Subject's decision to withdraw from the study.
5. Weight loss of >5% if not dieting and after consultation with the Sponsor, at the Investigator's discretion.
6. CDI-2 raw total score of 34, after consultation with a mental health professional, the Sponsor, and at the Investigator's discretion.
7. Requirement for use of prohibited concomitant medication after consultation with the Sponsor and Medical Monitor.
8. Subject's repeated failure to comply with protocol requirements or study related procedures.
9. The subject interrupts trial study drug application for more than 50% of scheduled doses.
10. Termination of the study by the Sponsor, FDA, or other regulatory authorities.

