### **ESTIMATING SEVERITY GRADE**

For abnormalities NOT found elsewhere in the Toxicity Tables use the scale below to estimate grade of severity:

**GRADE 1      Mild:** Transient or mild discomfort (<48 hours); no medical intervention/therapy required

**GRADE 2      Moderate:** Mild to moderate limitation in activity - some assistance may be needed; no or minimal medical intervention/therapy required

**GRADE 3      Severe:** Marked limitation in activity, some assistance usually required; medical intervention/therapy required hospitalizations possible.

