  - c. Subjects are approved to continue applying IP post Week 4 as long as the following have been discussed with the subject:

- Site should confirm the subject has adequate IP to continue dosing and if not ask the subject to return to the site to pick up additional IP or refer to the current IP Handling Plan for instructions on shipment of IP from site to subject.
- Confirm the subject has no AEs that would warrant discontinuation of the IP.
- Site should discuss any new or ongoing conmed(s) and determine if the use of any warrant having the subject stop IP application or not.
- For any female subject of childbearing potential that site should discuss and confirm the subject has continued her methods of ensuring pregnancy does not occur. Any deviation from these methods should be discussed further and the site should determine if IP should be halted or contact the medical monitor or Arcutis if they have any questions. A pregnancy test can be performed at the next onsite visit (this is applicable to prior visits being missed due to COVID-19 as well).
- Subjects are approved to continue dosing for up to 14 days past Week 4 until they return the clinic for the Week 4 visit. After this, sites should reach out to the Medical Monitor and/or Arcutis directly for approval to have subjects continue dosing.
- All the above discussions must be documented in the source.

d. If available, home health nurse visits could be considered for collection of Vital Signs and Clinical Labs.

e. In the event a subject is quarantined, has symptoms, or is confirmed positive for COVID-19, it is the Sponsor's opinion that IP can continue, assuming no other contraindications.

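### The creatinine Grade 3 band in Appendix 5 stops at 2.0 x ULN, so read literally the mandatory laboratory stopping rule in section 7.9 does not reach worse values (minor)

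*Protocol*

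**What the plan says.** Protocol section 7.9 lists events for which an individual subject's treatment will be discontinued. One is "A severe (Grade 3) laboratory abnormality (confirmed by repeat sample and considered related to study drug", with a reference to Appendix 5. The trigger names Grade 3. It does not say Grade 3 or higher.

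The Appendix 5 laboratory tables have three severity columns, and Grade 3 (severe) is the last. The creatinine row reads:

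- Grade 1: 0.7-1.0 x ULN
- Grade 2: 1.1-1.6 x ULN
- Grade 3: 1.7-2.0 x ULN

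Appendix 5 also has a general severity scale, introduced with "For abnormalities NOT found elsewhere in the Toxicity Tables use the scale below to estimate grade of severity". It grades by limitation of activity and need for treatment.

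Section 7.1.5 includes creatinine in the serum chemistry panel, scheduled at Screening, Baseline and Week 4, and allows unscheduled safety tests if the Investigator thinks them necessary. Appendix 6 adds a COVID-19 provision: "Subjects are approved to continue dosing for up to 14 days past Week 4". It also suggests home nurse visits for clinical laboratory samples.

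**The concern.** A mandatory stopping threshold should bind at least as firmly on a worse value as on a milder one. For creatinine, as printed, it does the opposite: the requirement holds in a band 0.3 x ULN wide (2.0 - 1.7) and lapses above it. No Grade 4 exists to catch the higher values.

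What is at stake is a written safety rule for children aged 6 to 11, to be applied at approximately 10 to 15 sites. A fixed rule is there so that the decision does not vary with the person reading the result. Above 2.0 x ULN that fixed element is missing and only judgement remains.

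**Working it through.** No sample-size or power calculation applies. The check is a count of table rows, followed by a literal application of the printed bands.

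**Step 1: count the graded rows for collected tests.** Inputs are the test list in section 7.1.5 and the Appendix 5 laboratory tables. Low and high directions count as separate rows, and the conditional urine microscopy counts as collected.

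- Chemistry: sodium 2, potassium 2, glucose 2, and one each for BUN, creatinine, albumin, alkaline phosphatase, AST, ALT, total bilirubin and direct bilirubin: 6 + 8 = 14.
- Haematology: white cells 2, and one each for haemoglobin, lymphocytes, neutrophils, eosinophils and platelets: 2 + 5 = 7.
- Urine: protein, glucose, blood = 3.
- Total: 14 + 7 + 3 = 24.

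**Step 2: classify the Grade 3 cells.** In 23 of the 24 rows Grade 3 is open-ended, for example AST and ALT >5 x ULN, BUN >35.5, haemoglobin <8.5 and platelets <50. One row, creatinine, is closed. Over all 37 laboratory rows in Appendix 5, five are closed: creatinine, magnesium, phosphate, PT and PTT. The last four are not collected under section 7.1.5.

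**Step 3: apply the rule.** Assume each value is confirmed by a repeat sample and judged related. As printed, the stop is required if 1.7 <= x <= 2.0. With an open top, it is required if x >= 1.7.

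| Creatinine (x ULN) | Grade as printed | Stop required as printed | Stop required with >=1.7 |
|---|---|---|---|
| 1.65 | none | no | no |
| 1.7 | 3 | yes | yes |
| 1.8 | 3 | yes | yes |
| 2.0 | 3 | yes | yes |
| 2.1 | none | no | yes |
| 2.5 | none | no | yes |
| 3.0 | none | no | yes |

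**Step 4: see whether other text restores the requirement.** The general severity scale does not: creatinine is in the tables, and the scale is functional, so it does not fit an increase without symptoms. The five-grade CTCAE scale in section 7.7.5 gives no creatinine cut-off, and the laboratory bullet does not refer to it.

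Five routes remain above 2.0 x ULN, all resting on judgement:

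1. Section 7.9, clinically significant laboratory values: "the Investigator should immediately contact the Medical Monitor to discuss if the subject should be discontinued from the study".
2. Section 7.9, discontinuation for an SAE, or for a clinically significant AE that the Principal Investigator or Medical Monitor thinks warrants it. Section 7.7.1 allows an AE to be "any unfavorable and unintended sign (including an abnormal laboratory finding").
3. Section 7.9, suspension: "Dosing of study drug for an individual subject may be suspended for safety concerns other than those described above".
4. Section 6.6, items 1 and 2, the second covering an AE that "represents an unacceptable risk to the subject if he/she continues in the study".
5. Appendix 6, before dosing continues past Week 4: "Confirm the subject has no AEs that would warrant discontinuation of the IP".

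**Step 5: find when the cell can act.** The only scheduled post-baseline laboratory draw is at Week 4 or early termination, when dosing normally ends. Scheduled post-baseline draws with dosing still planned: 0. That leaves unscheduled tests during treatment and tests during COVID-extended dosing.

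**Step 6: look for an effect on the analysis.** SAP section 10.7 summarises laboratory values descriptively and tabulates shifts relative to the normal range. It does not use Appendix 5 grades. SAP outputs affected: 0.

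**Step 7: read the rest of the row.** Grade 1 at 0.7-1.0 x ULN lies wholly at or below the upper limit of normal. Values between 1.0 and 1.1, and between 1.6 and 1.7, have no grade.

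**The case against.** The best reply is that the literal reading is not how anyone would act. Grade 3 is the top column and is labelled severe; no investigator would stop a child at 1.8 x ULN and regard a confirmed, related 2.5 x ULN as less than severe. The trigger is not purely mechanical either, since relatedness is itself a judgement. The neighbouring bullet on clinically significant AEs sits under the same mandatory wording, and the Medical Monitor must be contacted about clinically significant laboratory values. All of this stands, and it keeps the point minor. It does not make the printed threshold right.

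A second reply is that closed top bands recur in Appendix 5: four uncollected laboratory rows and, among clinical events, unintentional weight loss (>=9 to 20%). They may have come with the published tables that Appendix 5 names as its source. This also stands. A reader might infer from the count of 1 in 24 that creatinine is a proven isolated typing error; the documents do not show that. The count shows only that, among collected laboratory tests, this is the row where the closed top can affect conduct.

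A third reply is that the gaps at 1.0-1.1 and 1.6-1.7 disappear if multiples of ULN are rounded to one decimal. That is possible, but Appendix 5 states no rounding rule, and rounding would not help values such as 2.5 x ULN.

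**Conclusion.** The point holds as a minor error in a stated safety threshold. Among the 24 collected and graded laboratory rows, creatinine alone has a closed Grade 3, and as printed the mandatory bullet covers 1.7-2.0 x ULN and nothing higher.

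A reader might go further and infer that a child with a very high creatinine would be left on treatment. The documents do not support that: the judgement-based routes remain, and the intent is almost certainly that higher values are at least as severe. Nor do they support any effect on the PK, safety or efficacy summaries.

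The conclusion assumes a literal reading of section 7.9 and of the cell, and low and high directions counted as separate rows. The statement on reach assumes that dosing ends at Week 4 unless extended under Appendix 6. Treatment in the extension study ARQ-151-306 falls under a protocol that is not among these documents and is not considered here.

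**What to change.** In Appendix 5, print creatinine Grade 3 as >=1.7 x ULN. This keeps the printed floor, opens the top as in the other 23 collected rows, and brings 2.1, 2.5 and 3.0 x ULN under the rule. Section 7.9 can stay as it is.

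In the same edit, the sponsor's clinical team should check the whole creatinine row: confirm 1.7 as the cut-off, reconsider a Grade 1 band that covers normal values, and assign grades to 1.0-1.1 and 1.6-1.7 x ULN. How the upper gap is closed is a clinical choice. Extending Grade 2 upward leaves the mandatory threshold where it is, whereas lowering the Grade 3 floor would newly require stopping at values such as 1.65 x ULN.

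The cost is one table cell, and possibly the other two cells of that row, in the next protocol amendment. No new data, visits, procedures or SAP changes are needed.
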